1.4 INSTRUMENTATION

Two dimensional gait measurement system compose of;

1. 8meter walkway
2. Video camera
3. Personal computer

Calibrated ruler

Stop watch

Measuring wheel

Standard armchair (approximately 46 cm in height)

A 7.5 cm height step

Sphygmomanometer and stethoscope

Tape measure

Hand-held dynamometer

Oximeter

Metronome

1.5 PROCEDURE

All participants will be explained about details of the study and the interventions. After that, they will be asked to sign on the written consent approving by the committee of the institution prior to participate in study. All participants will be randomly allocated the participants into the experimental (SPCCT with MI) or the control (SPCCT with health education) groups. All participants will be screened following the criteria and will be collected the demographic data.

Both groups will receive the same program of SPCCT by physiotherapist who have 5 years experienced in neurological condition. Prior to training, tasks will be demonstrated using clear instructions. Seven lower extremity mobility tasks will be used in the SPCCT program. The tasks were selected from the study of Dean et al and adapted to be appropriate for improving gait function in patients with stroke. The trained tasks for the MI will be similar to the tasks in SPCCT to getting the transfer effects of training. The experimental group will receive MI training, whereas, the control group will receive health education which both will be provided by the researcher. Both groups will be matched for duration and frequency of the therapy sessions.

All outcome measures will be assessed by the therapist who have been trained the outcome measures of the study. As the primary outcome measurements, spatio-temporal variables will be measured by using two dimensional motion analysis method. The protocol of this method was proved to be valid and reliability from previous pilot study. For functional gait variables, six-minute walk test will be assessed for determining walking endurance, step test will be assessed for dynamic balance, and Timed Up and Go (TUG) test will be assessed for mobility function.

As the secondary outcome measure, the strength of hip flexor, hip extensor, knee flexor, knee extensor, ankle dorsiflexor, and ankle plantarflexor muscles will be assessed by using hand-held dynamometer. Muscle spasticity will be assessed by using the Modified Ashworth Scale (MAS). The outcome measures will be assessed at the baseline, after 2 weeks and 4 weeks intervention. For the safety, the therapist will measure blood pressure, pulse rate and fatigue level in the assessments, just before the training, and rest period during the training program.

1.6 INTERVENTION PROGRAM

Training schedule for the experimental and control groups

Experimental group	Duration (min)	Control group	Duration (min)
MI:			
- Relaxation	3		
- MI practice (Visual) 4 tasks	8.5	Health education	25
- Rest	2		
- MI practice (Kinesthetic) 4 tasks	8.5		

Experimental group	Duration (min)	Control group	Duration (min)
- Refocusing	3		
	25		25
TOCCT: - Warm up - TOCCT practice 7 tasks (4 min practice, 4 mins rest, 1 min transfer in a task)	3 62	TOCCT: -Warm up -TOCCT practice 7 tasks (4 min practice, 4 mins rest, 1 min transfer in a task)	3 62
	65		65
Total	90	Total	90

MI Training

The MI practice will be carried out in a quiet room of Physical Medicine and Rehabilitation, NRH clinic. In the MI training, there will be familiarization of the MI technique for 2 days in the 1st week and from other days of the 1st week up to 4th week, it will be the MI gait training. In MI gait training program, there will be 4 phases; 1) the body relaxation and awareness for 3 minutes, 2) visual imagery for 8.5 minutes, 3) kinesthetic imagery for 8.5 minutes, and 4) refocusing of body and environment for 3 minute. There will be 2 minutes rest period between the visual imagery and kinesthetic imagery. MI training during 4 weeks are described below;

1st week: Familiarization

The participants will be trained to familiarize with the MI tasks. The participants will be explained about the procedures. During the training, they are not supposed to perform the activity but only imagine about the tasks. Video will be used together with the explanation to perform and demonstrate about the tasks performing. After this session, the participants will perform the tasks physically. Then, the participants will be trained with both visual and kinesthetic MI tasks. Imagine the movement using the first person perspective both for visual imagery and the kinesthetic imagery. For the visual imagery, the participants will be requested to visualize their performing movements from inside of their body, as if they are looking through their own eyes while performing the movements. For the kinesthetic imagery, the participants will be requested to perceive their body sensations of the movements without any movement. During the MI practice, the participants will be asked to (a) avoid moving or contracting muscle from their leg, and keep a relaxed position (b) keep their eyes close throughout the practice (c) keep track of the number of sequences imagined with their fingers if necessary (d) if they lose their concentration during the practice, open their eyes, relax for a few moments and then continue the practice of the task. In the tasks of forward and then backward stepping tasks, the rhythm will be trained with metronome. In the walking tasks, the participants will be asked to walk along the 8 meters walkway and back towards the starting point and repeat the walking during the prescribed duration. The participants will be trained until they are able to reproduce the tasks correctly demonstrating declarative knowledge of the sequence.

2nd to 4th week Training

Stage 1: Body Relaxation and Awareness Stage

The participants will be asked to sit on the chair and the instructions will be given. They may open or close their eyes depend on preferring. Therapist will explain about two steps of the exercise. First, contraction of particular muscle group in the body. Next, releasing the tension and notice how the muscles feel in relaxation. The participants will be asked to contract their muscles when therapist say tense your muscle or move your body part, maintain this tension when therapist say hold, release this contraction when therapist say relax. Participants will be asked to maintain this relaxation up to the end of training.

Stage 2 and 3: Visual and Kinesthetic Imagery

There will be 4 specific gait MI tasks (Table 3.2). For the stepping task, progression will be provided by number of repetitions provided by the rhythm of the metronome. For the walking tasks, progression will be increased by the number of walking repetition in the walkway. The practice of the tasks will be assigned serially. Each task will be taken for 2 minutes. During the training, number of repetitions will be noted after finish the tasks and will be entered into the log-book using as a feedback for the next

practice session. The engagements of the MI practice will be checked by the pulse rate using the oximeter attached to the fingers of the affected hand. The fingers movements of the unaffected hand will be recorded for numbers of repetitions of the task completion during imagine. Moreover, during the imagery practice, therapist will ask participants to stop imagine unexpectedly and check position in the practice.

Training schedule for MI

MI tasks	Duration (min)
1. Stepping forward and backward onto block	2
2. Standing up from a chair, walking a short distance (3 m), and returning to the chair	2
3. Symmetrical walking (8 m)	2
4. Walking at fast speed (8 m)	2

Stage 4: Refocusing of Body and Environment

The instructions of the MI training according to the stages are described in the following;

Stages	Tasks
Stage 1	Body relaxation and awareness.
Stage 2	
Visual imagery
 
Task 1. Stepping forward and backward onto blocks; 1.a Stepping forward and backward onto the block with the unaffected leg 1.b Stepping forward and backward onto the block with the affected leg
 
Task 2. Standing up from a chair, walking a short distance, and returning to the chair
 
Task 3. Symmetrical walking
 
Task 4. Walking at fast speed

Stage 3	
Kinesthetic imagery
 
Task 1. Stepping forward and backward onto blocks 1.a Stepping forward and backward onto the block with the affected leg 1.b Stepping forward and backward onto the block with the affected leg
 
Task 2. Standing up from a chair, walking a short distance, and returning to the chair
 
Task 3. Symmetrical walking
 
Task 4. Walking at fast speed

Stage 4	Refocusing of body and environment.

Health Education (HE)

For the control group, they will receive 25 minutes of health education. The education will be provided by the researcher using the documents. One HE topic will take 2 treatment sessions and there will be 6 topics for the whole intervention period, 4 weeks. The training schedule for health education is described.

Topic	Duration (min)	Treatment session	Content
1. Changes caused by stroke	25	1 st and 2 nd	The most common general effects of stroke Common changes with a left-brain injury Common changes with a right-brain injury Common emotional effects of stroke Factors on which improvement depends
2. Complications after stroke	25	3 rd & 4 th	Common complications of stroke Treatments for complications after stroke
3. Emotional changes after stroke	25	5 th & 6 th	The way stroke cause emotional changes Some common emotional changes after stroke The way to cope changing emotion
4. Living at home after stroke	25	7 th & 8 th	Factors to going home Changes to do at home
5. High blood pressure (HBP) and stroke	25	9 th & 10 th	What is HBP? HBP and stroke risk Persons at higher risk for HBP.

Topic	Duration (min)	Treatment session	Content
6. Preventing recurrent stroke	25	11 th & 12 th	Controllable risk factors Uncontrollable risk factors Stroke warning signs

SPCCT

SPCCT program will include 7 different workstations intended to meaningful tasks related to gait performance. To get the effect of increasing therapy, it will involve the practice of higher levels of functional activities such as standing and walking. The training package will be provided according to participant's condition in terms of muscle strength and mobility status. The practice of the tasks will be serial in order. In the training the participants will be in the pairs. The practice will be as the distributed pattern. During the rest period of one participants who will observe the performance of partner and give encouragement to do the best. Each participant will receive activity log book in which the number of repetitions of performance will be entered and it will be used as the feedback in next station.

Training schedule of SPCCT is described in the following.

SPCCT details	Duration (min)
Warm up	3
1. Stepping forward-backward onto block	4 min practice, 4 min rest, 1 min transfer (9 min)
2. Stepping sideway onto block	9
3. Heel lifts in standing to strengthen affected planter-flexor muscles	9
4. Standing with a decreased base and reach for object	9
5. Standing up from a chair, walking a short distance, and returning to the chair	9
6. Symmetrical walking	9
7. Walking at fast speed	8
Total	65

Statistical analysis plan

Title: Effect of Structured Progressive Task-Oriented Circuit Class Training With Motor Imagery on Gait in Stroke

Clinical registration no: NCT03436810

Documentt date: January 18, 2017

Statistical analysis plan:

All data will be tested by the SPSS version 18.0 with a significant value of $p < 0.05$ for all comparisons. The demographic data of the participants will be presented with mean, standard deviation, and range for the continuous variables. Frequency and percentage will be presented for the categorical variables.

Normality will be tested by the Kolmogorov Smirnov Goodness of Fit test, for normally distributed variables, a two-way mixed repeated measure ANOVA will be tested to investigate the effect of group and time on the outcome measures. In addition, the interaction effect of the group by time will be detected. For the non-normally distributed variables, the Mann-Whitney U test (between-group) and the Friedman ANOVA test in conjunction with the Wilcoxon Signed-Rank test (within-group) will be used.

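### Every comparison is tested at an unadjusted 0.05 and no variable, visit or effect is named as deciding; the primary class alone carries an 8–10% chance of a false positive at two variables

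*SAP*

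**What the plan says.** **Threshold.** The SAP analyses all data "with a significant value of $p < 0.05$ for all comparisons". Neither document contains a hierarchy, an adjustment or a gatekeeping rule.

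**Tests.** For normally distributed variables, "a two-way mixed repeated measure ANOVA will be tested to investigate the effect of group and time on the outcome measures". The SAP continues: "In addition, the interaction effect of the group by time will be detected". Variables that fail the normality test get a Mann-Whitney comparison between groups, with no visit or change score specified.

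**Outcomes (Protocol 1.5, Procedure).**
- Primary: "As the primary outcome measurements, spatio-temporal variables will be measured by using two dimensional motion analysis method". The members of this class are not listed or counted.
- Next in the text: "For functional gait variables, six-minute walk test will be assessed for determining walking endurance, step test will be assessed for dynamic balance", followed by Timed Up and Go for mobility. These three tests are given no explicit rank.
- Then: "As the secondary outcome measure, the strength of hip flexor, hip extensor, knee flexor" and three further muscle groups, followed by spasticity on the Modified Ashworth Scale (MAS).

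**Visits.** "The outcome measures will be assessed at the baseline, after 2 weeks and 4 weeks intervention". None is singled out.

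**Objective.** The comparative objective in Protocol 1.1 (Summary) covers both the spatio-temporal and the functional gait variables.

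**The concern.** Three choices that define a primary analysis are open at once: which variable, which visit and which effect. Every candidate is judged at the same unadjusted 0.05. A significant result on any spatio-temporal variable, through the group effect or the interaction, could be presented as the primary finding without departing from the plan. The reader of the final report could not tell a prespecified answer from a selected one.

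At stake is the main inference of the trial, MI versus HE. The plan as written does not hold the false-positive rate at 5% two-sided, or at 2.5% in favour of MI, even within the class it labels primary.

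**Working it through.** The documents state no power, sample-size calculation or family-wise error rate, so there is no derived figure to reproduce. The only stated figure is the 0.05 per test, which is an input.

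**Inputs**
- Per-test level 0.05 (SAP). Sidedness is not stated. Two-sided is assumed, since the ANOVA F tests are non-directional; critical value c = 1.96.
- Number of variables k. The primary class is plural, so k is at least 2. Adding the three functional tests gives at least 5. A third case, k = 8, assumes five spatio-temporal variables; that count is not in the documents.
- Correlation r between variables: not in the documents. Assumed 0 to 0.8.
- 20 patients per arm, from the sex counts in Protocol 1.1 (15 + 5 and 11 + 9).
- Strength and MAS, labelled secondary, are not counted.

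**Step 1. One between-arm test per variable.** For independent variables the chance of at least one false positive is 1 − 0.95^k:
- k = 2: 1 − 0.9025 = 0.0975
- k = 5: 1 − 0.7738 = 0.226
- k = 8: 1 − 0.6634 = 0.337

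For equicorrelated normal test statistics,

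P = 1 − ∫ φ(u) [Φ((c − √r·u)/√(1−r)) − Φ((−c − √r·u)/√(1−r))]^k du,

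evaluated numerically. For errors in favour of MI only, the second Φ term is dropped.

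| k | Direction | r = 0 | r = 0.5 | r = 0.7 | r = 0.8 |
|---|---|---|---|---|---|
| 2 | either | 0.098 | 0.091 | 0.084 | 0.078 |
| 2 | favours MI | 0.049 | 0.045 | 0.042 | 0.039 |
| 5 | either | 0.226 | 0.183 | 0.148 | 0.127 |
| 5 | favours MI | 0.119 | 0.092 | 0.074 | 0.064 |
| 8 | either | 0.337 | 0.250 | 0.191 | 0.158 |
| 8 | favours MI | 0.183 | 0.125 | 0.095 | 0.079 |

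A simulation of two t-tests at 20 per arm gives 0.097 (r = 0) and 0.078 (r = 0.8), so the normal approximation is adequate here.

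**Step 2. Two effects on one variable.** Mixed ANOVA with no true effect, 20 per arm, three visits, compound symmetry, 100,000 trials. Either the group effect or the interaction has p < 0.05 in 0.096, 0.097 and 0.095 of trials at visit correlation 0.5, 0.7 and 0.9. A week-4 ANCOVA adjusted for baseline gives 0.050 at all three. If either effect counts on two variables, the rate is 0.186 (r = 0) to 0.151 (r = 0.8), at visit correlation 0.7.

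**Step 3. Which effect could decide.** Baseline is one of the three visits, so the group main effect averages in a visit at which randomised arms should not differ. The interaction has 2 degrees of freedom and identifies neither visit nor direction. Simulations of 50,000 trials, with assumed effects in SD at baseline/week 2/week 4 and visit correlation 0.5 and 0.7:
- 0/0.4/0.8: power 0.33 and 0.28 for the group effect, 0.60 and 0.82 for the interaction, 0.80 and 0.92 for week-4 ANCOVA.
- 0/0.8/0: the interaction is significant in 0.73 and 0.92 of trials, although nothing remains at week 4; week-4 ANCOVA in 0.05 and 0.05.

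**The case against.** The strongest reply has four parts.

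1. **No win rule is stated.** The chance of at least one false positive is the trial's error rate only if any one significant variable counts as success. This does not rescue the plan: declaring every comparison significant at 0.05 produces that family-wise rate directly. The either-effect figures in Step 2 are different. They rest on a rule that the plan neither states nor excludes, so they are illustrations.
2. **The inputs are assumed.** The correlation and the eight-variable case are not in the documents. This stands as a limit on precision. At r = 0.9 the two-variable figure is still 7.0%; only perfect correlation returns it to 5%. The 34% for eight variables is the independence limit, not an expected value.
3. **The interaction is a suitable planned test.** It does test whether change differs between arms. But the SAP adds it after the group effect and does not rank it. Naming the interaction on one variable would also hold 5%, but it would leave visit and direction open.
4. **ANCOVA is a preference, and the simulated scenarios favour it.** If the gain is reached by week 2 and kept (0/0.8/0.8), the gap narrows: interaction power 0.73 and 0.92, ANCOVA 0.80 and 0.93. ANCOVA is still no worse. It is a reasoned recommendation, not the only valid contrast. In the week-2-only scenario a significant interaction reflects a real difference, but not one at the end of the programme.

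It may also be too late to name a primary, because Protocol 1.1 describes the enrolled patients in the past tense. The fix has to allow for that.

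**Conclusion.** The concern holds, and the plan must be corrected. The MI versus HE objective has no deciding test, and the stated rule inflates the error rate when followed exactly.

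- **Primary class at its minimum of two variables:** 8–10% in either direction and 4–5% in favour of MI, against nominal 5% and 2.5%.
- **Gait family of the comparative objective, five variables at minimum:** 13–23%, and 18% at correlation 0.5.
- **Gait family of eight, if there are five spatio-temporal variables:** 16–34%, and 25% at correlation 0.5.
- **One variable, if either ANOVA effect were accepted:** about 10%.

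The first three ranges assume one two-sided test per variable and correlation from 0.8 down to 0. The absence of a named variable, visit, effect and multiplicity rule depends on none of these assumptions.

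**What to change.** First confirm that no between-arm outcome data have been examined. If so, amend the SAP and Protocol 1.5:

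1. List the spatio-temporal variables and name one as primary. The choice is the sponsor's.
2. Fix one deciding contrast: MI minus HE at week 4, adjusted for baseline by ANCOVA, two-sided 0.05, whatever the Kolmogorov-Smirnov test shows.
3. State the rank of the six-minute walk, step test and Timed Up and Go.
4. Replace the blanket 0.05 rule accordingly.
5. For the remaining gait variables, choose either one secondary family under Holm, or estimates with 95% confidence intervals and no significance claims.
6. Label the mixed-ANOVA effects, the nonparametric tests, week 2, strength and MAS as supportive.

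If between-arm outcomes have been seen, name no single primary, apply Holm over the whole gait family and label the analysis post hoc.

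**Cost.** Wording only; no new data. The primary keeps the full 0.05. Under Holm, power at the first-step threshold falls as below, for an effect with 80% power at 0.05 (d = 0.91, 20 per arm, t-test):

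| Use | Variables in the Holm family | First-step threshold | Power |
|---|---|---|---|
| Secondary family | 4 (5 less the primary) | 0.05/4 = 0.0125 | 0.60 |
| Secondary family | 7 (8 less the primary) | 0.05/7 = 0.0071 | 0.52 |
| Post hoc fallback | 5 | 0.05/5 = 0.01 | 0.57 |
| Post hoc fallback | 8 | 0.05/8 = 0.00625 | 0.50 |

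The estimates-only option has no threshold, but allows no claim on those variables. Under the fallback no result is confirmatory.

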1.1 SUMMARY

Title:	Effect of Structured Progressive Task-Oriented Circuit Class Training With Motor Imagery on Gait in Stroke
Clinical registration no:	NCT03436810
Document Date:	January 18, 2017
Study Description:	Structured Progressive Circuit Class Training (SPCCT) has developed on the basis of task-oriented therapy, provides the enriched benefits on the patients' motivation and motor function. Training with the Motor Imagery (MI) alone can improve gait performance in patients with stroke, but the better effect may observe if combined with the SPCCT. Thus, the aim of this study was to investigate the effect of MI with SPCCT on gait in patients with stroke. The study involved forty patients with stroke from 3 hospitals in Yangon, Myanmar. All participants received the 90 min intervention in a session. The experimental group received MI with SPCCT and control group received HE with SPCCT intervention 3 times a week for 4 weeks. The assessments were taken at the baseline, 2 week and 4 weeks after intervention. The outcomes measures involved spatio-temporal variables, walking endurance, dynamic balance, mobility function and muscle strength.
Objectives:	
General Objective: To investigate the effect of MI with SPCCT on gait performance in patients with stroke
 
Specific Objectives: To investigate the spatio-temporal and functional gait variables in patients with stroke after receiving MI with SPCCT
 
To investigate the spatio-temporal and functional gait variables in patients with stroke after receiving HE with SPCCT
 
To compare the effect of MI with SPCCT and HE with SPCCT on the spatio-temporal and functional gait variables in patients with stroke.

Outcome measures:	Spatio-temporal variables, walking endurance, dynamic balance, mobility function, muscle strength
Study Population:	Forty patients with stroke, age for experimental group was 49.90 ± 11.59 years and control group was 55.55 ± 10.74 years, 15 males and 5 females for experimental group and 11 males and 9 females for control group, Mean height for experimental group was 163.89 ± 6.55 centimeters and control group was 162.03 ± 13.04 centimeters. Mean weight for experimental group was 63.65 ± 6.63 kilograms and control group was 63.35 ± 13.04 kilograms

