1.2 METHODS

Participants

All participants will be diagnosed as a stroke and will be recruited from the departments of the Neuromedical and Physical Medicine and Rehabilitation, Yangon General Hospital (YGH) and the National Rehabilitation Hospital (NRH) in Yangon, Myanmar. Eligible participants will be randomly allocated into either the experimental or control groups. For allocation of the participants, a computer-generated list of random number will be used. In order to maintain recruitment balance between groups throughout the trial, a permuted block randomization process will be used within each strata using block sizes of at least 2 with all blocks divisible by 2. The sequence generation and allocation concealment will be managed by the researcher. To prevent inadequate concealment of allocation sequence, properly randomizing method using sequentially numbered, opaque sealed envelopes (SNOSE) will be used in this study. The allocation envelope will be prepared by using the aluminum foil and carbon paper. The aluminum foil will be used to ensure opaque and the allocation sheet inside cannot read against the light. The carbon paper will be used to prevent violations of allocation concealment. The treatment allocation sheet of standardized-size paper will be fold to fit with envelop. Place 1 sheet of carbon paper on top of the folded allocation sheet with the carbon side facing the paper so that writing on the front of the envelop is transferred to the treatment allocation paper inside. Then place this carbon paper and allocation sheet together inside aluminum foil wrapper. Finally, place complete insert into the envelope properly (290). Group assignment will be communicated directly to the therapist for the implementation on a single participant basis. In this study, the assessments will be done by the researcher. The assessor and the participants will be blinded from the study.

Study Design

The study design will be a randomized double blind balanced parallel-group (1:1).

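### The SAP commits only to significance tests at p < 0.05 and pre-specifies no MI-minus-HE estimate or confidence interval for any outcome

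*SAP*

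**What the plan says.** The third specific objective (Protocol 1.1, Objectives) is the randomised comparison: "To compare the effect of MI with SPCCT and HE with SPCCT on the spatio-temporal and functional gait variables in patients with stroke". Outcomes are assessed at baseline, 2 weeks and 4 weeks (Protocol 1.5).

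The SAP is two paragraphs long. Its only stated criterion is a test result, "with a significant value of $p < 0.05$ for all comparisons". For normally distributed variables, "a two-way mixed repeated measure ANOVA will be tested to investigate the effect of group and time on the outcome measures", and the group-by-time interaction is to be detected. For the others it names "the Mann-Whitney U test (between-group) and the Friedman ANOVA test in conjunction with the Wilcoxon Signed-Rank test (within-group"). It does not say which visit the between-group rank test uses, or whether it is applied to final values or to changes.

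Means, standard deviations and ranges are promised for demographic data only. Neither document mentions a confidence interval, a between-arm mean or median difference, a difference regarded as important, or how a non-significant result is to be read.

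**The concern.** None of the planned tests, reported as a test, states how far apart the arms are.

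- With three visits, the group-by-time term is an F test with 2 numerator degrees of freedom. It indicates whether the two profiles differ, but not by how much, in which direction or at which visit.
- Mann-Whitney, as planned, yields a p-value and no shift.
- Friedman and Wilcoxon work within an arm and do not address the comparison.

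Followed as written, the plan therefore commits to significant or not significant for its only randomised question. A p-value above 0.05 may mean that any benefit of MI is small, or that 40 patients could not settle the matter. Only an estimate with its interval separates the two. A p-value below 0.05 would likewise come with no planned statement of how large or how uncertain the difference is. Several outcomes at two follow-up visits also leave the choice of contrast open until the data have been seen.

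**Working it through.** **No figure to reproduce.** The documents give no sample-size calculation, target difference, outcome SD or power, so results are in SD units.

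**Inputs from the documents**
- Total of 40: "The study involved forty patients with stroke from 3 hospitals in Yangon, Myanmar" (Protocol 1.1).
- Arms: "15 males and 5 females for experimental group and 11 males and 9 females for control group" (Protocol 1.1), that is 15 + 5 = 20 and 11 + 9 = 20.
- Threshold 0.05 (SAP); three visits (Protocol 1.5).

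**Assumptions, not in the documents**
- Two-sided test, no dropout, normal outcome, and the same SD in both arms and at all visits.
- Correlation r between visits, shown at 0.3, 0.5, 0.7 and 0.9.

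**Step 1. Half-width of the 95% interval for MI minus HE, in SD units**

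The common factor is √(2/20) = 0.3162.

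- Difference in change from baseline: t(0.975, 38) × √(2/20) × √(2(1 − r)) = 2.0244 × 0.3162 × √(2(1 − r)) = 0.6402 × √(2(1 − r)).
- Difference at 4 weeks with baseline as covariate: t(0.975, 37) × √(2/20) × √(1 − r²) = 2.0262 × 0.3162 × √(1 − r²) = 0.6407 × √(1 − r²).

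| r | √(2(1 − r)) | Change score | √(1 − r²) | Baseline-adjusted |
|---|---|---|---|---|
| 0.3 | 1.1832 | 0.76 | 0.9539 | 0.61 |
| 0.5 | 1.0000 | 0.64 | 0.8660 | 0.55 |
| 0.7 | 0.7746 | 0.50 | 0.7141 | 0.46 |
| 0.9 | 0.4472 | 0.29 | 0.4359 | 0.28 |

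At r = 0.5, for example, an observed difference in change of exactly zero would still be compatible with a true difference of up to 0.64 SD either way.

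**Step 2. Power of the planned group-by-time test for a true 0.5 SD difference at 4 weeks**

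Further assumptions: the between-arm difference grows linearly (0, 0.25 and 0.5 SD at the three visits), and correlations are equal between all pairs of visits (compound symmetry).

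- Mean difference over visits: 0.25. Sum of squared deviations: 0.0625 + 0 + 0.0625 = 0.125.
- Noncentrality: λ = (20/2) × 0.125 / (1 − r) = 1.25 / (1 − r).
- Reference distribution: F with (3 − 1) = 2 and (40 − 2) × 2 = 76 degrees of freedom; 5% critical value 3.12.

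| r | λ | Power | Chance of p ≥ 0.05 |
|---|---|---|---|
| 0.3 | 1.79 | 20% | 80% |
| 0.5 | 2.50 | 26% | 74% |
| 0.7 | 4.17 | 42% | 58% |
| 0.9 | 12.50 | 88% | 12% |

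Unless the correlation between visits is high, a real 0.5 SD benefit would miss p < 0.05 more often than not. The p-value alone would not show whether that had happened.

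**The case against.** The strongest reply is that this is a short plan, silent on reporting, rather than a wrong method. Several parts of that reply stand.

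- A reader might infer that the sponsor will take p ≥ 0.05 to mean that MI adds nothing. No passage says so. The SAP sets a significance level and gives no rule for interpreting a null result, and it makes no equivalence claim. What can be said is that nothing in the plan guards against that reading.
- A reader might infer that the third objective demands an effect size that the trial will never produce. The objective speaks of comparing effects and names no effect size. The ANOVA is fitted to arm-by-visit means, so the difference can be derived from the planned model. The accurate statement is that no estimate is pre-specified for reporting.
- A reader might attach one power figure to the trial from a simple two-sample t test at a single visit. For normal variables that is not the planned test. The power of the planned test depends heavily on a correlation that the documents do not give, and at r = 0.9 it is good for a 0.5 SD difference.
- Imprecision comes from the sample size. Reporting an interval reveals it and does not cure it.

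The reply does not remove the core. That software could print a difference is not a commitment to report it, nor does it fix the contrast, visit or adjustment. On the rank-test path, the Mann-Whitney test as planned supplies no estimate at all.

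**Conclusion.** The concern holds in this form: on both analysis paths the SAP pre-specifies tests only, so the planned output for the randomised comparison gives neither size nor precision, and a non-significant result could not be distinguished from an inconclusive one.

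This matters in a trial of 20 per arm because the interval could be wide: about 0.3 to 0.8 SD either side for a change score as r falls from 0.9 to 0.3, and slightly narrower with baseline adjustment. Power for a true 0.5 SD difference runs from 88% down to 20% over the same range. These figures rest on the assumptions listed above; dropout would worsen them. They describe one comparison and do not establish that the trial is underpowered, since neither r nor a target difference is stated.

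The sponsor should make the change. It alters what can be concluded on the third objective, but leaves the design and data collection untouched.

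**What to change.** Amend the SAP as follows.

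1. For each outcome, pre-specify one between-arm contrast with its 95% confidence interval: the MI-minus-HE difference at 4 weeks adjusted for baseline, or alternatively the difference in change from baseline to 4 weeks. Choose one and state it. At every correlation tabulated, the adjusted version gives the narrower interval.
2. For variables analysed by ranks, report the Hodges-Lehmann shift in change from baseline with its 95% confidence interval.
3. Base the conclusion on the third objective on the estimate and interval. Describe p ≥ 0.05 as inconclusive unless the interval excludes a difference named in advance as important.

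The planned tests can stay alongside. The cost is SAP wording and a few extra output lines; the Hodges-Lehmann interval may need a routine outside the named package. No new patients, visits or data are needed.
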